### 1.2 Secondary Aims

- 1.2.1 to assess disease-specific lymphedema patients’ response to propranolol
- 1.2.1a to assess *subjective* patient-reported lymphedema-related symptoms
  - i) Validated questionnaires: LYMPH—ICF, LYMPH—ICF--LL
- 1.2.1b to assess *objective* measures
  - i) Physical examination: Weight, BMI, limb girth discrepancy
  - ii) Imaging evaluation: MRI
  - iii) Blood and tissue analysis: circulating and tissue biomarkers
  - iv) Genetic analysis: correlation of somatic mutations to propranolol response

Table 2. Primary and secondary endpoints

## 2.0 BACKGROUND

	Primary Endpoint (Aim 1)	Secondary Endpoint (Aim 2)
Subjective Assessment	Questionnaires QOL	Questionnaires
	Short Form 36 Lymph-ICF Lymph-ICF-LL	Symptoms (Drainage, pain) Activity levels Clothing size change
Objective Assessment	Clinical and radiological Exam	Clinical and radiological Exam
	Blood pressure Heart rate Blood sugar Whole Body MRI QMR Deuterium and NaBr	Weight, BMI Limb girth discrepancy CTCAE Grading for Lymphedema Imaging: QMR, whole body MRI Blood and Tissues Circulation biomarkers IHC lymphatic vessel phenotype PIK3CA mutational analysis Next Gen sequencing analysis

## 2.1 Introduction/Rationale for Development

Primary lymphedema is a vascular malformation of the lymphatic system, or a lymphatic malformation (LM)[6]. In lymphedema, regional edema develops, most commonly in the lower extremities, although it can affect any location[7, 8]. Primary lymphedema is classified based on the age of onset: congenital, childhood (praecox), and adulthood (tarda)[9]. Primary lymphedema with early onset (excluding tarda) is considered rare and estimated to affect 1.2/100,000 people under the age of 20[9], while another study reported a 1/6000 incidence for primary lymphedema presenting under the age of 36[10]. Since adult-onset of primary lymphedema is defined to occur after 35, these data possibly underestimate the true incidence.

Lymphatics function to maintain tissue fluid homeostasis, immune surveillance and lipid uptake from the intestines. Defective lymphatic development can cause both mass effects and physiologic derangements. Over time, the abnormal lymphatic drainage leads to chronic, progressive swelling of tissues, increased adipose deposition and fibrosis[8], interfering with ambulation and use of the affected extremity. Such abnormal lymphatic tissue also harbors pools of lymph, which do not drain or circulate normally, and are consequently static and prone to severe infections. Cutaneous involvement can lead to weeping of lymph or blood-tinged lymph from skin lesions. Psychological trauma can be experienced by these patients, who may struggle with the social isolation consequent to physical differences and repeated illness[7-9]. Collectively, co-morbidities of lymphedema include pain, swelling, lymph leakage, hyperkeratosis, interference with function, cellulitis and sepsis and produce a severe lifelong burden of disease associated with significant morbidities.

Because LM pathobiology is poorly understood, existing treatments are largely empirical, and often ineffective. Furthermore, there are no objective diagnostic tools. Treatment options are limited and ranges from lymphatic massage, compression garments, diuretics[11, 12], to surgery[13], only with partial success. Residual tissue after incomplete resection is prone to recur when infectious or inflammatory stimuli occur, and recurrence is frequent. Without effective diagnostic tools, any response to treatment can not be documented or quantified. *Patients with primary lymphedema are frequently therapeutic orphans and new approaches to treatment are desperately needed.* Interest in identifying medical treatments has been great, although limited by the lack of knowledge of the basic pathophysiology of these lesions.

Recently our laboratory has identified two cell types in LMs: lymphatic malformation progenitor cells (LMPCs) and lymphatic malformation endothelial cells (LMECs) that are potential therapeutic targets as they can both recapitulate the LM phenotype in our LM mouse model[14]. In a screen of different drugs using LMPCs, we identified propranolol, a non-selective pan-beta adrenergic receptor ( $\beta$ AR) inhibitor, as a candidate for lymphedema/LM treatment. We find low levels of  $\beta$ 2AR expression in normal lymphatic endothelium, and high levels of  $\beta$ 1AR/ $\beta$ 2AR expression in LMPC/ECs of LM tissues. *In vitro*, propranolol suppresses LMPC/EC proliferation, and in our LM mouse model, propranolol decreases the abnormal lymphatic vessel dilation that is associated with lymphatic vessel dysfunction. *These data suggest that propranolol normalizes LM vessel phenotype, possibly by decreasing LM cell proliferation.*

In addition to our laboratory studies, there are prior anecdotal reports of propranolol efficacy in children with lymphatic anomalies[15-18]. More recently, it has become the therapy of choice for infants and children with complicated hemangiomas[19], and FDA approval for Hemangeol (March 2014) as a treatment for infantile hemangiomas heralded the first time any medications has obtained FDA approval in treatment of a vascular anomaly. Based on our pre-clinical data, published anecdotal reports of efficacy

against lymphatic anomalies, FDA approval for treatment of a vascular anomaly, and the lack of effective treatments led us to offer propranolol to families of severely affected patients.

## 2.2 Preclinical Studies

### 2.2.1 Anti Lymphatic Malformation Activity

Our laboratory has used a cytotoxicity assay to screen for candidate molecules for use against LMPCs and LMECs. Our results demonstrated that propranolol was cytotoxic against both LMPCs and LMECs with an LD50 300-500 $\mu$ m. At lower concentrations (50-100 $\mu$ m), propranolol had anti-proliferative effects on both LMPCs and LMECs, and in LMPCs upregulated transcript expression of lymphatic endothelial differentiation genes (Prox1, podoplanin, VEGFR-2, VEGFR-3, and LYVE1) in a dose-dependent manner (range 10-100 $\mu$ m). When LMPCs were injected into nude mice, the development of dilated lymphatic channels was disrupted in mice that were treated with propranolol (6mg/kg/day) when compared to control mice. In mice the improved lymphatic vessel phenotype correlated with reduced infiltration of inflammatory macrophages. Thus, both *in vitro* and *in vivo* pre-clinical data demonstrated propranolol was efficacious against LM formation and LM physiology.

### 2.2.2 Animal Toxicology (if applicable)

Preliminary results in our laboratory treating immunosuppressed mice in our

murine LM model demonstrated that these mice tolerated up to 40mg/kg/day of propranolol by echocardiography. Based on general clinical observations, these mice continued to behave normally, without signs of weight loss, lethargy, or mortalities. Propranolol has been used in other murine studies with no reported toxicities or intolerance reported[24, 25]. We have found that 6mg/kg/day, a dose far below the 40mg/kg/day, in a mouse model was sufficient to improve LM vessel abnormalities. Using equivalent surface area dosage conversion factors, 6mg/kg/day in a mouse correlated to 3.3-4.8mg/kg/day, higher than the 0.7-1mg/kg/day we used to treat our patients (<https://ncifrederick.cancer.gov/lasp/acuc/frederick/Media/Documents/ACUC42.pdf>, accessed Nov 7, 2015)[26, 27].

### 2.2.3 Preclinical Pharmacokinetic Studies

Preliminary *in vitro* studies performed in our laboratory has shown that propranolol had anti-proliferative effects in “low-dose” range (in the nanomolar range:  $10^{-9}$  to  $10^{-7}$ M). However, as propranolol dosage is increased, it exhibits cytotoxic effects on cells (in the micromolar range:  $10^{-6}$  to  $10^{-4}$ M). The anti-proliferative effects were also accompanied by a dose-dependent decrease in cAMP activity. The cytotoxic dose range coincided with increased MAPK activation (ERK 1/2). Our results are consistent with other reports that propranolol had partial agonist effects with MAPK activation [Azzi, Baker, Galandrin].

The dose range of propranolol used to treat infantile hemangiomas ranged from 1-3mg/kg/day. This correlates to plasma concentration of 21-448ng/mL (private communication, [name]) corresponding to  $10^{-6}$  to  $10^{-5}$ M dose range. In adults given 0.5-1mg/kg/day, an average of 50ng/mL was achieved[28, 29]. This correlates to approximately  $10^{-6}$ M range. We propose to study patient responses at 2- to 3-mg/kg/day, corresponding to  $10^{-6}$  to  $10^{-5}$ M, within the  $10^{-6}$  to  $10^{-4}$  anti-proliferative dose range.

## 2.3 **Pediatric Studies**

### 2.3.1 Prior Experience in Children

Recent reviews of the activity of propranolol in children with vascular anomalies report apparent efficacy in infantile hemangioma[19, 20, 30], and anecdotal experience with lymphatic malformations of the tongue and other anatomic locations[15-18]. The biologic basis for these effects is not known, but is hypothesized to relate to role of beta-adrenergic receptors in regulation of angiogenic factor expression[31-35]. Our pilot biologic studies of cells derived from lymphatic malformations suggest that beta-adrenergic signaling functions as survival pathway in both lymphatic progenitor and lymphatic endothelial cells.

### 2.3.2 Risk Assessment

#### 2.3.2.1 Hypotension and Bradycardia:

Studies have shown that the peak effect of oral propranolol on blood pressure and heart rate occurs 1 to 3 hours after it is taken[28, 29]. As such, current recommendations are that patients should have HR and BP done at baseline and also hourly for the first 2 hours after a dose increase, and at least once after the target dose is achieved. As dose response is generally most significant after the first dose, once normal vitals are obtained with the first dose there is no recommendation that vitals should be re-checked at the same dose level, unless the patient is very young, has cardiovascular issues or co-morbidities, or if clinical complaints arise.

Pediatric patients must have vitals within the normal range for their age group, and adults with normal established vitals, prior to starting a dose. Dose escalations will take

place as given in the table above. Patient must have no evidence of clinical contraindications with acceptable HR and BP parameters prior to dose escalation occurring. If individuals are found to have a fall in their blood pressure or heart rate outside of normal range, they will have dose de-escalation to the prior tolerated dose level. If they are able to tolerate this lower dose level with normal parameters and no clinical symptomatology they will have a re-challenge of the dose escalation after 2 weeks. If on re-escalation they once again have fall in HR and blood pressure, they will again undergo dose de-escalation to the prior tolerated dose level for 2 weeks and re-evaluated again until the end of the 8-week study. If the patients are already at the lowest doses, they will be given a 2-week rest and re-evaluated after 2 weeks. If HR and BP then fall within normal parameters they will be reintroduced to the study at the lowest study dose of propranolol. If patient is once again found to have fall in HR/BP below normal parameters for age upon an attempt to re-start propranolol, they will be removed from the study. That is, all patients who do not tolerate a dose increase for the 2nd time will be held at the last tolerated dose until the end of the study. If a patient cannot tolerate the lowest doses twice, they will be removed from the study.

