#### **5.2.2 Intra-Patient Escalation**

The starting dose will be 1 mg/kg/day (BID) with dose escalation up to 3 mg/kg/day (BID) in the absence of clinical contra-indications. There will be no escalations beyond 3 mg/kg/day (Table 1).

At the return visit, patients must have no evidence of clinical contraindications with normal HR and BP parameters prior to dose escalation occurring. They will be re-evaluated 2 hours after the first escalated dose. If individuals have normal heart rate and blood pressure and report no clinical symptoms (dizziness, increased fatigue), they will be given the new escalated dose and re-evaluated 2 hours after the new dose. If their HR and BP are within normal limits (WNL), they will be sent home on this new escalated dose and will return in another 2 weeks for evaluation. If individuals are found to have a fall in their blood pressure or heart rate below the normal value at 2 hours after the new dose, they will not be escalated and will be sent home at the current dose. They will return in 2 weeks for evaluation for dose escalation.

If individuals are found to have a fall in their blood pressure or heart rate below the normal value at the return visit *and* clinically asymptomatic, they will be held at the current tolerated dose level (no escalation). If they are able to tolerate this lower dose level with normal parameters and no clinical symptomatology they will return for evaluation of dose escalation at the next visit. If their parameters are WNL, they will be escalated and evaluated. If they do not tolerate dose escalation, they will be held at the current tolerated dose of propranolol until the end of the study without further attempts to escalate. Patients who are not able to tolerate dose escalation at 2 consecutive visits will have no more dose escalation challenges and stay for the remainder of the study at the current tolerated dose.

Individuals found to have a fall in HR and BP below normal parameters at initiation (0.5mg/kg/day, week 1) will be removed from the study for 1 week. At week 2 they will be re-evaluated. If HR and BP are within normal parameters they will be reintroduced to the study. If patient is once again found to have fall in HR/BP below normal parameters upon an attempt to re-initiate (failed the lowest initiation dose of 0.5mg/kg/day twice), they will be removed from the study.

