## 6.0 DOSE MODIFICATIONS FOR ADVERSE EVENTS

**The Study Chair must be notified of any dosage modification.**

### 6.1 Dose Modifications for Potential Propranolol Specific Side Effects

#### 6.1.1 Hypotension and Bradycardia

**Baseline blood pressure (BP)** is defined as the blood pressure obtained at the examination used for study enrollment. This baseline BP should be obtained as follows: 1) Obtain 3 serial blood pressures from the same extremity with the patient in the same position that are separated by at least 5 minutes. Avoid using the lower extremity if possible. BP will not be obtained from the affected limb. 2) Average the systolic blood pressure from the 2nd and 3rd measurements. 3) Average the diastolic blood pressure from the 2nd and 3rd measurements. 4) The baseline BP is the average of the systolic over the average of the diastolic measurements.

Heart rate will be measured by palpation of the radial pulse serially from the same extremity for 15 secs, separated by at least 5 minutes. In the case of extremity LMs, pulse rate will not be obtained from the affected limb. 2) Average the pulse rate from 2nd and 3rd measurements.

6.1.1.1 Patient must have no evidence of clinical contraindications with normal HR and BP parameters prior to dose escalation occurring. If individuals are found to have a fall in their blood pressure or heart rate to below normal limits, but asymptomatic:

- a. patient will be not have dose escalation
- b. patient will be evaluated for dose escalation at the next 2-week cycle.
- c. if HR and BP fall below normal ranges and patient is symptomatic, propranolol will be held for 2 weeks, and re-introduced at the next visit at the lowest tolerated dose.
- d. if patient is at the lowest dose already (0.5mg/kg/day), they will be pulled from the study and re-evaluated at the next visit.
- e. Patients receiving 0.5mg/kg/day who experience HR or BP decrease below the normal range at 4 weeks must be taken off protocol therapy.

Table 5. Side effects and propranolol dosing guidelines

Hypotension and Bradycardia	Propanolol Dosing Guidelines
Within normative range	No change in dose
Below normal range, asymptomatic	Cardiology evaluation, EKG, echocardiogram; if cardiac status is acceptable, patient will not have dose escalation and remain at current dose level with subsequent re-evaluation at 2 weeks

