Below normal range, symptomatic	Discontinue propranolol (off protocol therapy. Re-evaluate after 2 weeks. If HR and BP then fall within normal parameters they will be reintroduced to the study with dose de-escalation to the prior tolerated dose of propranolol. If HR/BP below normative range at 0.5mg/kg/day, patient will be removed from study)

Hypoglycemia	Management/Next Dose for propranolol
Blood glucose >80 mg/dl	No change in dose
Blood glucose <80, >60, asymptomatic	Clinical evaluation, review feeding schedule, repeat test after more

Hypoglycemia	Management/Next Dose for propranolol
	frequent/supplemental feeds
Blood glucose <80, symptomatic	Discontinue propranolol (off protocol therapy)

Bronchospasm	Management/Next Dose for propranolol
Transient/self-limited episode	Clinical evaluation, may continue at same dose
Associated with URI	Hold propranolol till URI resolves; if >7 days, off protocol
Not associated with URI, persistent or requiring new medical treatment	Discontinue propranolol (off protocol therapy)

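### The heart-rate and blood-pressure dose rules contradict each other, chiefly at 0.5 mg/kg/day, so staff cannot follow all of them

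*Combined protocol and SAP*

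**What the plan says.** **Fall after the first 0.5 mg/kg/day dose.** Section 2.4 rests the patient off drug for 2 weeks and then re-challenges. The last paragraph of 5.2.2 takes the patient off for 1 week and re-evaluates at week 2. Section 2.3.2.1 sides with 2.4 on length: "If the patients are already at the lowest doses, they will be given a 2-week rest and re-evaluated after 2 weeks".

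**Asymptomatic below-normal reading at a return visit.** Section 5.2.2 says of these patients: "they will be held at the current tolerated dose level (no escalation". Section 6.1.1.1 opens with a "fall in their blood pressure or heart rate to below normal limits, but asymptomatic", and its item (a) withholds escalation. The asymptomatic row of Table 5, once cardiac status is judged acceptable, says "patient will not have dose escalation and remain at current dose level with subsequent re-evaluation at 2 weeks".

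**The same reading on 0.5 mg/kg/day.** The lettered list in 6.1.1.1 adds (d), "if patient is at the lowest dose already (0.5mg/kg/day), they will be pulled from the study and re-evaluated at the next visit", and (e), "Patients receiving 0.5mg/kg/day who experience HR or BP decrease below the normal range at 4 weeks must be taken off protocol therapy". Table 5 removes at this dose only in its symptomatic row: "If HR/BP below normative range at 0.5mg/kg/day, patient will be removed from study".

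**Fall in general.** Section 2.3.2.1, directly after the check of vital signs before escalation, says that if readings fall "outside of normal range, they will have dose de-escalation to the prior tolerated dose level".

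**Two failed challenges.** Sections 5.2.2 and 2.3.2.1 hold the patient at the last tolerated dose to the end of the study. Section 14.2.3 does this for the higher levels, but withdraws a patient who twice fails the step to 1 mg/kg/day.

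**The concern.** A low heart rate or blood pressure is a foreseeable effect of the drug, and Table 6 schedules vital signs at weeks 1, 2, 4, 6 and 8, so these rules are consulted at every escalation visit. They decide which dose the patient takes next and, at 0.5 mg/kg/day, whether the patient stays on treatment.

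That bears on what the trial reports. Section 11.2.2 makes tolerability of escalating doses the primary endpoint. Section 8.4 reports toxicity rates at each dose tested and evaluates response among patients at the highest tolerable dose. The week-8 MRI, QMR, body-water, biopsy and questionnaire assessments are made at whatever dose the rules produced. If two patients with the same event are managed under different sections, the dose each is said to tolerate reflects the section used as well as the drug.

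**Working it through.** **Planned ladder.** Section 5.1 gives 0.5, 1, 2 and 3 mg/kg/day, with steps at weeks 2, 4 and 6. With no fall, a trace returns 3 mg/kg/day in weeks 6-8, as planned. At 14 days per step the total is 14 × (0.5 + 1 + 2 + 3) = 91 mg/kg.

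**1. Rest after a fall at initiation.** The two periods differ by 1 week, which is 1/8 = 12.5% of the maximum treatment time. On 5.2.2's count, week 1 to week 2 is one week, so a 2-week rest ends at week 3, when Table 6 schedules no vital signs. Suppose later steps are tolerated, one level per scheduled visit:
- 5.2.2: 0.5 at week 2, 1 at week 4, 2 at week 6.
- 2.4, restart put back to week 4: 0.5 at week 4, 1 at week 6.
- 2.4, unscheduled restart at week 3: 0.5 at week 3, 1 at week 4, 2 at week 6.

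The final dose therefore differs by one level or not at all, depending on something 2.4 leaves open.

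**2. Asymptomatic reading on 0.5 mg/kg/day at week 4.** A patient can be on 0.5 at week 4 after a below-normal reading at week 2, after failing the first 1 mg/kg/day dose, or after restarting at week 2 under 5.2.2. Section 5.2.2 and Table 5's asymptomatic row hold the dose. Item (e) ends protocol therapy and states no symptom condition. Both cannot be followed. Item (d) is weaker evidence: it follows (c), which has switched to symptomatic patients, and it matches Table 5's symptomatic row.

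**3. Two failed challenges to 1 mg/kg/day.** Under 5.2.2 and 2.3.2.1 the patient stays on 0.5; under 14.2.3 the patient leaves. Section 14.2.3 labels 1 mg/kg/day the lowest study dose, and 5.2.2 opens by giving 1 mg/kg/day as the starting dose, although 5.1 and 5.2.2's own last paragraph start at 0.5. That may be the source of the mismatch.

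**4. Literal reading of 2.3.2.1.** Assume one asymptomatic fall at a return visit, recovery by the next visit, re-challenge to the dose that was lowered, and no step at week 8. Doses are those taken from weeks 1, 2, 4 and 6.

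| Fall at | 2.3.2.1, literal | Hold rule | Weeks 6-8 |
|---|---|---|---|
| week 2, on 0.5 | 0.5, 0, 0.5, 1 | 0.5, 0.5, 1, 2 | 1 vs 2 |
| week 4, on 1 | 0.5, 1, 0.5, 1 | 0.5, 1, 1, 2 | 1 vs 2 |
| week 6, on 2 | 0.5, 1, 2, 1 | 0.5, 1, 2, 2 | 1 vs 2 |

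Totals at 14 days per step:
- Week-4 fall: 14 × 3 = 42 against 14 × 4.5 = 63 mg/kg, ratio 1.50.
- Week-6 fall: 14 × 4.5 = 63 against 14 × 5.5 = 77 mg/kg, ratio 1.22.

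With only 7 days on the first step, each total drops by 7 × 0.5 = 3.5: 38.5 against 59.5 (1.55) and 59.5 against 73.5 (1.24). If re-challenge after the week-4 fall went straight to 2 mg/kg/day, both rules would end at 2, with totals of 14 × (0.5 + 1 + 0.5 + 2) = 56 against 63. The week-6 row does not depend on that choice.

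**The case against.** The strongest reply concerns 2.3.2.1. Its paragraphs are about dose increases: monitoring after an increase, re-challenge, re-escalation, and a closing summary about patients who fail an increase a second time. Read that way, it agrees with 2.4 and 5.2.2, which return the patient to the previous dose after a failed first escalated dose, and the differences in step 4 disappear. It is also a risk assessment in the background chapter, and 10.1 refers adverse-event removals to Section 6.0. This largely stands. A reader might infer that the plan requires a lower dose for asymptomatic return-visit patients. The documents do not support more than saying that the sentence lacks the limit it needs.

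A second reply is discretion. The Table 1 footnote lists staying, stepping down or stopping as options, the principal investigator prescribes after cardiology evaluation, and patients are registered at one university. That reduces inconsistency between staff, but it does not tell the prescriber which rule applies. Nor does the pointer to Section 6.0 settle step 2, since (e) and Table 5 both sit there.

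Third, (e) resembles 14.2.3: a patient still on 0.5 at week 4 has usually missed a step already, so removal may be intended. If so, Table 5 and 5.2.2 are the texts that need changing.

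Fourth, 11.5 keeps every eligible patient who took propranolol in the main response analysis, and 10.1 continues follow-up off therapy. One patient is 1/20 = 5.0% to 1/15 = 6.7% of the planned 15-20. A reader might infer that a removal loses that share of the analysis. It does not by itself, although week-8 measurements could be missing or made off drug.

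**Conclusion.** The rules contradict each other and should be reconciled. Three conflicts rest on the text alone: 1 or 2 weeks off after a fall at initiation; hold or stop for an asymptomatic reading on 0.5 mg/kg/day at week 4; and hold or withdraw after two failed challenges to 1 mg/kg/day. The first is worth one week of an eight-week course. The other two decide whether a patient stays on treatment.

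The return-visit conflict with 2.3.2.1 is conditional. The 1 against 2 mg/kg/day in weeks 6-8 is a worst case that needs the literal reading, a single transient fall and no step at week 8; the week-4 row also needs re-challenge to the lowered dose only.

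Frequency cannot be estimated. A reader might take Table 7's rates and infer a chance of at least one event between 1 − (1 − 0.028)^15 = 35% and 1 − (1 − 0.028 − 0.009)^20 = 53%. Those rates come from infantile hemangioma and do not separate return-visit falls from first-dose falls, many of which create no conflict. Adding the two rates also assumes that no patient has both events. No estimate or confidence interval has been shown to change. This is a minor to moderate wording matter.

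**What to change.** - **2.3.2.1:** limit the de-escalation sentence to falls after the first escalated dose, and refer return-visit falls to Table 5.
- **6.1.1.1(d) and (e):** state that both apply only to symptomatic patients, as in Table 5. If asymptomatic removal is intended, amend Table 5 and 5.2.2 instead.
- **2.4 and 5.2.2:** use one rest period after a fall at initiation. One week fits the scheduled week-2 visit. If 2 weeks is chosen, say whether the restart is at week 3 or week 4, and bring 2.3.2.1 into line with whichever is kept.
- **14.2.3:** align with 5.2.2 and 2.3.2.1 on what happens after two failed challenges to 1 mg/kg/day, and name 0.5 mg/kg/day consistently as the lowest dose.

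The cost is a wording amendment, with no new tests or patients, and no new visits if the 1-week rest is kept. The downside is that, under the hold rule, an asymptomatic patient with below-normal readings stays on the current dose until the next visit, after the cardiology evaluation that Table 5 already requires. The sponsor should confirm that this is intended.
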